13.1.2 Secondary Endpoints

13.1.2.1 R0 Resection Rate

R0 resection rate is defined as the proportion of patients in whom an achieved R0 resection was achieved during surgery (see [Section 11.7.2](#)). The R0 resection rate will be estimated in two cohorts, 1) patients who signed the consent form, deemed eligible by central review, and received any protocol defined treatment in each arm and 2) patients who signed the consent form, deemed eligible by central review, and underwent surgery in each arm. The R0 resection rate will be estimated by the number of patients in whom R0 resection was performed divided by total number of patients in cohort 1) and cohort 2) in each arm.

13.1.2.2 Event-free Survival

Event-free survival is defined as time from randomization to the first documentation of event where events considered are 1) disease progression, per RECIST, prior to surgery, 2) surgery with R2 resection, 3) recurrent disease following surgery, or 4) death due to any cause.

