7.3.3 Surgical Quality Control

Sites scheduling patients for surgery should notify the study chair of their intent to operate at the time the operation is scheduled. This notification should consist of an email to the study chair with the Alliance patient ID number and date of surgery, along with contact information of the site treating surgeon and credited study PI on the OPEN form.

For all patients who undergo surgery during protocol treatment (including resection or not), the Study Chair and Surgical Co-chair will review the preoperative CT scan, the operative note, the surgical pathology report, and the adverse events associated with surgery (30 days postoperative) within 60 days of surgery. This requires that sites upload the required source documentation in a timely manner (see [Section 6.1.1](#)), and complete the AE CRF without delinquency.

Specific attention will be paid to deviations as listed above, as well as adverse events that occur in association with surgery. Operative reports and outcomes which, in the opinion of the Study Chair and Surgical Co-chair, raise potential patient safety concerns will be discussed and reviewed with the credited study PI immediately. Two operations which lead to such a discussion may lead to the site being restricted from enrolling future patients.

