11.4.3.1 Evaluation of Elevated CA19-9 Levels (When Present)

Note: this evaluation will be done for each patient for descriptive purposes only and will not be used to evaluate the secondary endpoint of progression free survival. Decision making for the efficacy of therapy and for relapse or progression must be based on imaging. Biochemical progression without the demonstration of objective progression of target or non-target lesion will not be sufficient indication to remove the patient from the study (refer to [Section 13.1](#)).

Biochemical Response (B-RESP): Reduction in elevated CA 19-9 level by at least 50% of normalization of an elevated value, confirmed with 2 successive measures.

Biochemical Progression (B-PROG): Increase in elevated CA 19-9 level by 50%, confirmed with 2 successive measures. If patient has had biochemical response as defined above, then subsequent biochemical progression is defined as >50% increase from the lowest recorded level while on study.

Biochemical Stability (B-STAB): Elevated CA 19-9 level does not change enough to qualify as response or progression.

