11.8 Treatment Evaluation after Completion of Surgery and Post-operative Chemotherapy

11.8.1 The term “recurrence” is used if cancer returns either in the locoregional area of the primary tumor or at distant sites following R0 or R1 resection.

11.8.2 Recurrence is determined radiographically and biopsy need not be performed except as detailed below or when CT findings are equivocal in the determination of the enrolling physician.

Locoregional Recurrence: identified by a new soft-tissue mass around the mesenteric vasculature or regional lymph nodes. Note that soft-tissue in this location on early postoperative scans may be benign and due to postoperative changes. Such findings may be difficult to distinguish from early tumor progression. In cases in which the diagnosis is ambiguous, discussion with the PI should occur. Performance of tissue biopsy should be considered prior to assigning a diagnosis of locoregional recurrent disease.

Distant Recurrence: identified by a new hypodensity in the liver or nodule(s) in the lungs or peritoneum. Other sites of presumptive distant recurrence (adrenal, brain) should require prompt biopsy confirmation. New ascites should be interrogated with aspiration and cytology if it is an isolated finding and should not necessarily be taken to indicate carcinomatosis, particularly following the performance of resection and reconstruction of the mesenteric vein(s).

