12.1.2 Disease Progression

Remove from protocol therapy any patient with disease progression as per [Section 12.1.3](#) or recurrence after surgery (either Arm 1 or Arm 2 patients). Document details, including tumor measurements, on data forms.

After disease progression, patients should be followed for survival per the study calendar ([Section 5.0](#)).

Note: Biochemical progression (B-PROG) without the demonstration of objective progression (PD) of target or non-target lesion will not be sufficient indication to remove the patient from the study (see [Section 11.4.3](#)).

12.1.3 Removal of Patients from Protocol Therapy:

In the absence of treatment delays due to adverse events, treatment will be completed unless the patient experiences any one of the following scenarios. The specific indication should be described as:

- Metastatic disease identified on imaging studies
- For patients with RECIST PD with local progression only, the treating investigator should decide whether continuing protocol treatment is in the best interest of the patient
- The presence of locally advanced disease on pre-surgical restaging imaging studies (see [Appendix II](#) for definition of locally advanced pancreatic cancer)
- Decline in PS in the absence of radiographic evidence for disease progression if PS cannot be recovered (symptomatic deterioration)
- Metastatic disease identified intraoperatively and biopsy-proven
- Unresectable disease identified intraoperatively (e.g., locally infiltrative disease without metastases for which the surgeon does not feel resection is safe)
- R2 surgical resection
- Nontherapeutic (aborted) operation for any other reason
- Intercurrent illness that prevents further administration of treatment
- Unacceptable adverse event(s)
- Patient decides to withdraw from the study
- General or specific changes in the patient's condition that render the patient unacceptable for further treatment in the judgment of the investigator

Patient should be removed from protocol therapy, and followed as per [Section 5.0](#), post-treatment follow-up. Protocol treatment will be discontinued and further treatment is at the discretion of the treating physician.

12.1.4 Follow-up for Patients Removed from Protocol Therapy:

For patients who are removed from protocol therapy in any instance listed in [Section 12.1.3](#), follow patients per the schedule found in [Section 5.0](#) of the protocol for clinical and survival status.

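### The event-free survival definition has no event for an operation aborted because of metastatic or unresectable disease, so on its literal wording these patients stay event-free until death and EFS is biased upward

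*Combined protocol and SAP*

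**What the plan says.** Section 13.1.2.2 measures EFS from randomization to the first of four events: "1) disease progression, per RECIST, prior to surgery, 2) surgery with R2 resection, 3) recurrent disease following surgery", and, fourth, death from any cause. The list is closed.

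Three other places fix what these terms cover:

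- Section 11.8.1 says recurrence is the term "if cancer returns either in the locoregional area of the primary tumor or at distant sites following R0 or R1 resection".
- Sections 7.3.1.6 and 11.7.2 define R2 as tumor removal that is macroscopically incomplete, so some resection must have taken place.
- Section 7.3.3 words its review requirement as "For all patients who undergo surgery during protocol treatment (including resection or not", so an operation without resection is still surgery there.

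The protocol foresees the missing outcome. Section 7.3.1.5 tells the surgeon when to abort. Section 12.1.3 lists "Metastatic disease identified intraoperatively and biopsy-proven" and "Unresectable disease identified intraoperatively" as reasons for leaving protocol therapy, each on its own line, separate from R2 resection and from other aborted operations.

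Section 13.4.2.1 plans Kaplan-Meier estimates of EFS by arm and a log-rank comparison. It gives no censoring rule and no rule for aborted operations.

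**The concern.** Two groups of patients leave the operating room with known gross disease. Those with an R2 resection have an EFS event that day. Those whose operation was abandoned for metastatic or unresectable disease have none. Their later tumor growth is not progression before surgery, because surgery has taken place, and it is not recurrence, because there was no R0 or R1 resection. They accrue event-free time until they die.

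Leaving an event out can only lengthen a patient's EFS, so the error in each arm's EFS curve runs upward. The wording is also loose enough that two analysts could date the same patient's event at laparotomy, at a later scan, or at death.

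**Working it through.** **Which event could apply to a patient aborted for metastatic or unresectable disease?**

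| Event in 13.1.2.2 | Does it apply? |
|---|---|
| 1. RECIST progression before surgery | Not to anything after the operation, since 7.3.3 counts it as surgery. The operative finding is made at surgery and is not an imaging assessment. |
| 2. R2 resection | No. No tumor was removed, and 12.1.3 lists these outcomes separately from R2. |
| 3. Recurrence after surgery | No. 11.8.1 requires an R0 or R1 resection. |
| 4. Death | Yes. |

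**The plan's figure for patients exposed to the gap.** Section 13.2 expects 40% to leave treatment before surgery: 134 × 0.60 = 80.4, which reproduces the stated 80. Per arm, 62 × 0.60 = 37.2. The plan states no event count or power for EFS, so there is no EFS figure to reproduce.

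**Inputs for the size of the effect**

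- Aborted share of operations, a: not in the documents; assumed 5-25%.
- Time of surgery: eight 14-day cycles (16 weeks) plus 4-8 weeks (Section 7.0) is 20-24 weeks, or 4.6-5.5 months; taken as 5 months.
- Median OS of unresected patients: 15.4 months (Section 1.4.2) and 12.3 months (Section 1.4.9), taken as measured from randomization.
- Survival after the aborted operation: assumed exponential, with remaining median 12.3 − 5 = 7.3 months or 15.4 − 5 = 10.4 months.

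**Formula.** Compared with counting the event at surgery, EFS at month t is overstated by (80 × a / 134) × P(alive at t | aborted at month 5).

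Probability alive:

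- At 12 months: 0.5^(7/7.3) = 0.514 and 0.5^(7/10.4) = 0.627.
- At 18 months: 0.5^(13/7.3) = 0.291 and 0.5^(13/10.4) = 0.420.

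| Aborted share (assumed) | Patients of 134 | Share of all | 12-month overstatement, points | 18-month overstatement, points |
|---|---|---|---|---|
| 5% | 4 | 3.0% | 1.5-1.9 | 0.9-1.3 |
| 10% | 8 | 6.0% | 3.1-3.7 | 1.7-2.5 |
| 20% | 16 | 11.9% | 6.1-7.5 | 3.5-5.0 |
| 25% | 20 | 14.9% | 7.7-9.4 | 4.3-6.3 |

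Per arm of 62, the range is about 2 patients (37.2 × 0.05 = 1.9) to 9 patients (37.2 × 0.25 = 9.3). For each of them the event falls about 7-10 months late at the median (7.3 to 10.4 months).

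**The case against.** The best defense is that the text is ambiguous and that a sensible analyst would read it kindly.

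*Surgery may mean resection.* Section 7.3 opens by describing surgery as resection of the primary tumor and regional nodes, and Section 6.2.2 ties specimen requirements for operated patients to the resection. On that reading a never-resected patient is always before surgery, and later RECIST progression is event 1. Section 7.3.3 points the other way, and the EFS definition does not choose. Even on the kinder reading, the event moves only to a later scan. The last sentence of the study calendar's follow-up footnote asks only for survival information once a patient is removed from treatment, although Section 12.1.4 asks for clinical and survival status.

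*An intraoperative metastasis may already be progression.* Section 11.4.3 makes a new malignant lesion progressive disease, Section 7.3.1.5 calls for biopsy, and Section 12.1.2 refers to Section 12.1.3 for progression. The statement "Decision making for the efficacy of therapy and for relapse or progression must be based on imaging" comes from the CA19-9 subsection, where the contrast is with biochemical change, so it carries limited weight. This argument has some force for metastases, less for local unresectability. But Section 12.1.3 cannot serve as a definition of progression, because it also lists withdrawal and intercurrent illness. And a lesion found at operation is not plainly found before it.

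These readings show the wording is unclear. Neither is stated as the EFS rule.

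*The between-arm effect.* A reader might infer that the arm with more aborted operations would look better. The documents do not support that. That arm's EFS would be inflated more, but its patients still have deaths as events, and Section 1.4.9 cites a median OS of 12.3 months in unresected patients against 19.3 months after margin-negative resection. In addition, Arm 2 closed to enrollment, and its treatment stopped, on 08/13/2018, although Section 13.4.2.1 keeps the log-rank test.

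**Conclusion.** The gap is real on the literal text, and its direction within an arm is certain: EFS is overstated wherever operations are aborted for metastatic or unresectable disease. Arm 1's estimate is exposed whatever becomes of the comparison.

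The size is not known. It is about 1.5-9.4 points at 12 months for an assumed 5-25% aborted, and about 3-7.5 points at 10-20%. This rests on the assumed rate, exponential survival after surgery at about 5 months, and medians from cited series whose starting points and unresected patients may not match this trial's. It would be smaller if later progression were counted under the kinder reading. A reader who supposed that most of these patients, say 70-90%, are alive at 12 months would get a larger figure, but the protocol's cited medians give 51-63%.

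EFS is secondary. The primary 18-month OS rate and the interim rule on R0 resection do not use it. The definition should be corrected before the EFS analysis.

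**What to change.** 1. Extend event 2 to R2 resection, or operation without resection because of metastatic or unresectable disease, dated at surgery from the operative report.
2. State that RECIST progression is an event at any time in a patient without an R0 or R1 resection, where imaging is available.
3. Reconcile the calendar footnote (survival information only after removal from treatment) with Section 12.1.4 (clinical and survival status), so that it is clear which data EFS can draw on in these patients.
4. Add a sensitivity analysis that counts only metastatic disease found at operation.

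The first change is wording: Section 7.3.3 already has the operative note reviewed for every operation, resected or not. The second is not free of data needs. It depends on scans that the calendar footnote does not clearly require after removal, and operative reports cannot supply them. Dating the event at surgery largely avoids that dependence.

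There are two downsides. EFS becomes slightly less favorable. And local unresectability would count when found at laparotomy but not when found only on pre-surgical restaging without RECIST progression, although Section 12.1.3 removes both kinds of patient. The sensitivity analysis shows how much that asymmetry matters.

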13.1.2.3 Pathologic Complete Response (pCR) Rate

Pathologic complete response (pCR) rate is defined as the proportion of patients in whom a pCR was confirmed by histopathologic review of the surgical specimen (see [Section 11.6](#)) The pCR rate will be estimated in two cohorts, 1) patients who signed the consent form, deemed eligible by central review, and received any protocol-defined treatment in each arm and 2) patients who signed the consent form, deemed eligible by central review, and underwent surgery. The pCR rate will be estimated by the number of patients in whom a pCR was confirmed divided by total number of patients in cohort 1) and cohort 2) in each arm.

13.1.2.4 Adverse Events (AE)

AEs and the maximum grade for each type of adverse events will be recorded for each patient separately for the following 3 periods:

1. During neoadjuvant chemotherapy and chemoradiation therapy
2. Surgical complications during surgery and post-op period for 90 days or prior to adjuvant therapy
3. During adjuvant therapy. See [Section 9.1](#).

Similarly, scores (0-4) and maximum score for each PRO-CTCAE item will be recorded for each patient separately for the 3 periods.

13.2 Sample Size

We anticipate enrolling a maximum of 124 evaluable patients (62 per arm) per statistical design. Additional 10 (5 per arm) patients will be accrued to account for cancelations, ineligibilities, major violations, and lost-to-follow up, etc. Thus the total targeted accrual will be 134 patients.

We anticipate to pre-register 5 patients per month. Since we estimate 80% of patients who are pre-registered for central review will be randomized to therapy, the actual accrual will be 4 patients per month. Thus, we expect to pre-register 168 patients to reach the targeted accrual of 134 patients. The accrual period of this study is estimated to be 34 months.

We also expect that 40% of patients randomized to therapy will be off protocol treatment prior to surgery (i.e. will not undergo surgery). Therefore we expect that of the 134 patients, 80 will proceed to surgery. The primary endpoint, overall survival at 18 month post randomization, is well-defined even among patients who do not receive surgery. Therefore, the percentages of patients who do not undergo surgery do not affect the trial design.

13.3 Power Justification

The primary aim of this randomized phase II study is to evaluate 18-month OS rate in patients with borderline resectable cancer of the head of the pancreas treated neoadjuvantly using one of the following regimens: 1) Arm 1: 8 cycles of systemic FOLFIRINOX or 2) Arm 2: 7 cycles - of systemic FOLFIRINOX followed by short-course hypofractionated radiation therapy. All patients who are able to undergo subsequent surgery will also receive 4 cycles of postoperative FOLFOX. Eligible patients will be randomized and stratified by ECOG performance score onto two arms. Within each arm, single-arm sequential design with one interim analysis for futility will be implemented. The final efficacy analysis and interim analysis will be based on 18-month OS rate and R0 resection rate, respectively, and evaluated in each arm separately. The comparison of OS between arms will be carried out only if both arms are deemed promising at the end of the trial. “Pick-a-winner” strategy will be implemented to choose one treatment strategy for recommendation.

An extensive literature review was conducted to evaluate median OS and R0 resection rate in patients purported to have “borderline resectable” tumors who received chemo, chemoRT, etc. were conducted. Twenty-six studies published between 2004 and 2015 are identified with number of borderline resectable patients range from 8 to 129. All but three of these studies are retrospective studies.

The following table summarizes the historical data of median OS and R0 resection rate among all patients started treatment, including both patients with and without surgery.

Time era	Among Studies with N > 20				Among Studies with N > 50			
	N of studies	Weighted	Median	Range (IQR)	N of studies	Weighted	Median	Range (IQR)
Median OS in months								
Prior to 2012	6	21.3	21.5	14.2 – 25 (18.0 – 22.8)	3	22.0	22.0	14.2 – 25 (21.5 – 22.5)
2012 and later	9	21.2	19.9	17.2 – 28 (18.0 – 23.6)	6	21.2	21.0	17.2 – 28 (17.9 – 23.2)
All studies	15	21.2	21.0	14.2 – 28 (17.6 – 23.3)	9	21.5	22.0	15 – 28 (19.0 – 23.0)
R0 Resection Rate Among All Patients Started Neoadjuvant Treatment								
Prior to 2012	6	41.4%	36.9%	30 – 59%	3	43.0%	38.8%	30 – 59%
2012 and later	9	61.2%	54.4%	42 – 92%	6	60.0%	54.2%	42 – 92%
All studies	15	53.0%	53.4%	30 – 92%	9	52.8%	53.9%	37 – 92%

We consider studies with reasonable number of borderline resectable patients (e.g. N > 20, and/or N > 50) to estimate the historical estimates of the median OS and R0 resection rate for sample size and power determinations. There is substantial variability in the literature reported median OS across studies. The median OS reported in these studies varies from 14 to 28 months, with a median of 21 to 22 months and an interquartile range of about 18 to 23 months. Most of the previous studies are retrospective single-institution studies subject to patient selection bias, which likely to skew the reported OS higher. Thus, we consider the median OS of at most 18 months (equivalent to 18m OS rate of 0.50, assuming exponential survival function) which is the lower bound of the IQR of literature reported data as the null hypothesis. To demonstrate clinical meaningful improvement in OS, we target an alternative hypothesis of median OS of at least 27 months (equivalent to 18m OS rate of 0.63; a 50% increase in median OS time).

The summary data in the table shows clear increase trend of R0 resection rate over time. For interim analysis based on R0 resection rate, if R0 resection rate is at least 60% (null hypothesis) based on weighted R0 resection rate from historical data, the arm warrants continuing to full accrual for OS final analysis. If the observed R0 resection rate is significantly less than 60%, we consider early futility of the arm and stop accrual of patients onto that arm. Therefore, the interim analysis based on R0 resection rate will be testing alternative hypothesis of R0 resection rate $\leq 40\%$ against the null hypothesis of R0 resection rate $\geq 60\%$.

The study operating characteristics were assessed by simulation studies based on the estimation procedures and decision rules specified for final and interim analysis described in [Section 13.4.1](#). A maximum of 62 evaluable patients in each arm will provide 82% power to detect an improvement of 13% in 18 months OS rate, i.e., testing alternative hypothesis that the 18 months OS rate is at least 63% against the null hypothesis that the 18 months OS rate is at most 50%, at a one-sided significance level of 0.07. The probability of stopping accrual at interim is 43% and 0.8% if the true R0 resection rate is 40% and 60%, respectively.

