1.2 Rationale for Trial Design

Herein we propose to evaluate the efficacy of two rational neoadjuvant treatment backbones in a randomized study. The study builds upon our previous work as requested by CTEP and will define standard preoperative treatment regimens to which future novel regimens can and will be compared in subsequent randomized trials.

We have proposed a randomized frequentist design using exact binomial distribution for this study. This design focuses on evaluating whether clinically meaningful improvement of survival rate can be achieved by the tested regimens comparing to historical data. The evaluation of each treatment arm will be conducted separately, based on a practical assessment of whether the arm is “clinically relevant” alone, as well as the outcome comparisons between two treatments if both arms are deemed promising at the end of the trial. This study uses a critically important interim endpoint (R0 resection rate) that is different from the final endpoint (18 month OS rate) and an interim analysis which allows elimination of any futile arm after only 30 patients enrolled to that arm. If both arms are deemed promising at the end of the trial, a pick-a-winner strategy will be employed to choose one arm as the “winner”. Using a fast maturing end point, R0 resection rate, for interim analysis prevent the possibility of halting the trial at interim analysis while the whole study still powered to detect clinical meaningful improvement in OS rate.

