13.4.1.1 Interim Analysis

One interim analysis will be performed to assess treatment futility for each arm separately. For each given treatment arm, the R0 resection rate will be evaluated when surgical data become available for first 30 evaluable patients, approximately 8 months after trial activation. If at most 11 patients (i.e. ≤ 11 patients) among 30 evaluable patients underwent R0 resection, then the given treatment arm will be deemed not promising and the accrual to this treatment arm will be terminated. An evaluable patient is defined as any patient who signed informed consent, deemed eligible by central review and received any protocol-defined treatment.

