13.4.1.2 Final Analysis

The primary efficacy analysis will be performed on 18-month OS rate for the two treatment arms, separately, based on all evaluable patients. For each given treatment arm, if full accrual is reached and at least 36 patients (i.e. ≥ 36 patients) out of 62 evaluable patients are alive up to 18 months after randomization, the regimen of the evaluated arm will be considered worthy of further testing in this disease population. Otherwise, the regimen will be deemed inefficacious. The final analysis will be carried out approximately 18 months after the last patient, in each arm, is enrolled. This will occur approximately 52 months after trial activation.

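### The one-sided level of 0.07 in Section 13.3 is not the level of the stated null: over 18-month OS of at most 50%, the rule of 36 or more alive out of 62 has a maximum error of 0.126

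*Combined protocol and SAP*

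**What the plan says.** Section 13.3 states 82% power at an 18-month OS rate of 63% with 62 evaluable patients per arm, tested "against the null hypothesis that the 18 months OS rate is at most 50%, at a one-sided significance level of 0.07". On the source of these figures it says: "The study operating characteristics were assessed by simulation studies based on the estimation procedures and decision rules specified for final and interim analysis". The endpoints of the two stages differ: "The final efficacy analysis and interim analysis will be based on 18-month OS rate and R0 resection rate, respectively".

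The rules are in Section 13.4.1. At the interim, if 11 or fewer of the first 30 evaluable patients have an R0 resection, "then the given treatment arm will be deemed not promising and the accrual to this treatment arm will be terminated". At the final analysis the arm succeeds if "at least 36 patients (i.e. ≥ 36 patients) out of 62 evaluable patients are alive up to 18 months after randomization".

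R0 has its own interim hypotheses in Section 13.3, with R0 of 60% or more as the null and 40% or less as the alternative. The only operating characteristics tied to an R0 rate are the stopping probabilities: "The probability of stopping accrual at interim is 43% and 0.8% if the true R0 resection rate is 40% and 60%, respectively". No R0 rate is attached to the 0.07 or to the 82%. Section 1.2 describes the design in these terms: "We have proposed a randomized frequentist design using exact binomial distribution for this study".

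**The concern.** A significance level quoted for a null that constrains OS alone should bound the false-positive rate for every R0 rate compatible with that null. The final cut-off by itself has an error well above 0.07 at OS 50%. The interim stop brings the error down to about 0.07 only if the R0 rate is low, and a low R0 rate also removes much of the power.

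The rule is the formal efficacy decision for an arm. Under Section 1.3, if only one arm passes, it becomes the control arm for later randomized trials. Someone reading Section 13.3 will take 0.07, about 1 in 14, as the chance that a regimen with 50% survival at 18 months passes. At R0 60% it is about 1 in 8, and nothing else in the document corrects that impression.

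**Working it through.** **Inputs.** Final rule: 36 or more alive of 62 (13.4.1.2). Interim stop: 11 or fewer R0 of 30 (13.4.1.1). OS null 50% and alternative 63% (13.3). R0 rates: 40% and 60% from the interim hypotheses; the weighted 53.0% (all studies) and 60.0–61.2% (2012 and later) from the table block "R0 Resection Rate Among All Patients Started Neoadjuvant Treatment" in 13.3. R0 50% is added as an intermediate value.

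**Step 1: the plan's own stopping probabilities.**
- P(X ≤ 11 | 30, 0.40) = 0.431, printed as 43%.
- P(X ≤ 11 | 30, 0.60) = 0.0083, printed as 0.8%.

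Both reproduce.

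**Step 2: the final rule alone.**
- Error: P(X ≥ 36 | 62, 0.50) = 0.1264.
- Power: P(X ≥ 36 | 62, 0.63) = 0.8258.

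A futility stop can only remove successes. So 0.1264 is the maximum error at OS 50% whatever the R0 rate and however R0 relates to survival, and it is smaller for OS below 50%. Neighbouring cut-offs do not give 0.07 either: 37 or more gives 0.081, and 38 or more gives 0.049.

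**Step 3: both stages, stop binding, R0 independent of survival.** Each entry is (1 − stop probability) × the Step 2 value. For example, at R0 40% the error is (1 − 0.4311) × 0.1264 = 0.0719.

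| True R0 | Stop probability | Error at OS 50% | Power at OS 63% |
|---|---|---|---|
| 40% | 0.4311 | 0.0719 | 47.0% |
| 50% | 0.1002 | 0.1138 | 74.3% |
| 53% | 0.0536 | 0.1196 | 78.2% |
| 60% | 0.0083 | 0.1254 | 81.9% |
| 61.2% | 0.0057 | 0.1257 | 82.1% |

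The printed 0.07 appears at R0 of about 40%, and the printed 82% at about 60%.

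**Step 4: can one R0 rate give both?** On a fine grid under independence, the error rounds to 0.07 for R0 of 38.8–40.5%, where power is 43–49%. Power rounds to 82% for R0 of 58.5–65.8%, where the error is 0.125–0.126. The two ranges do not overlap.

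**Step 5: without assuming independence.**
- At R0 60% the stop can remove at most 0.0083, so the error lies between 0.1264 − 0.0083 = 0.118 and 0.126.
- At R0 40% power cannot exceed 1 − 0.431 = 56.9%.

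At those two rates the mismatch holds under any dependence.

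**Step 6: sensitivity of the 0.07 to dependence.** The 18-month survival splits here are assumptions, because the documents give none; overall OS is held at 50%. At R0 40%, survival of 60% in R0 patients against 43% in the others gives an error of 0.081; 75% against 33% gives 0.094; 85% against 27% gives 0.102. Other settings also land near 0.07, such as R0 38% with 60% against 44% (0.070). The sponsor's scenario therefore cannot be read back from the printed figure.

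**The case against.** The best defence is that the 0.07 is a design-level figure from simulating both stages: error at a jointly unfavourable point (OS 50%, R0 40%) and power at a jointly favourable one (OS 63%, R0 60%). Both R0 rates are the protocol's own, and the sentence directly after the 0.07 uses exactly these two. On that reading, needing two R0 rates is expected and the calculation is sound; the defect is an unstated condition.

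It is true that 0.07 need not be a miscalculation, since 0.0719 reproduces at that point under independence. The reading does not rescue the text, however. No such joint null is stated, the printed null names OS only, and Section 13.3 labels R0 of 60% or more as the interim null. An arm with good R0 and 50% survival falls inside the stated null, and it is a realistic case: the pilot in Section 1.4.4 reported 18-month OS of 50% and 14 margin-negative operations among 22 treated patients (64%).

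Two limits on the concern do stand. First, the comparison with historical R0 uses the all-study and the 2012-and-later rows. The pre-2012 weighted rates of 41.4% and 43.0% give errors of 0.080 and 0.088, closer to 0.07, although Section 13.3 itself notes that R0 rates have risen. Second, Arm 2 closed on 08/13/2018 and Section 13.4.1.2 applies the rule only at full accrual, so in practice the decision concerns Arm 1.

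**Conclusion.** The concern holds. For the null as written, the maximum one-sided error is 0.126, not 0.07; this is an exact binomial result that needs no assumption about R0 or its relation to survival. At weighted R0 rates of 53.0% to 61.2%, with a binding stop and independence, the error is 0.120 to 0.126, which is 0.120/0.07 = 1.7 to 0.126/0.07 = 1.8 times the printed level. The printed 82% power is right for R0 of about 60%, but the error there is at least 0.118 under any dependence. The 0.07 is at best the error at one favourable point within the null. Which point the sponsor simulated is not known.

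**What to change.** Keep the rule, the cut-off and the sample size. In Section 13.3, replace the phrase giving the 0.07 level with wording such as:

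> the maximum one-sided type I error at 18-month OS 50% is 0.126 (0.125 including the interim if the true R0 rate is 60%; about 0.07 if the true R0 rate is 40% and R0 is independent of survival); power at OS 63% is 82% if the true R0 rate is 60%

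These conditional figures are true of the rules as written; they should not be presented as the sponsor's derivation. The sponsor should confirm the R0 rates and the R0–survival dependence used in its simulation.

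The cost is one phrase and that confirmation. The disclosed error is less favourable than the printed one, so the change does not loosen the design.
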